A PROSPECTIVE CONTROLLED MULTI-CENTER STUDY ON VANGUARD™ COMPLETE KNEE & VANGUARD™ HIGH FLEX RP KNEE

GENERAL INFORMATION

Principal Investigators

[name]., Ph.D. – 75 Cases
[name]., Ph.D. – 75 Cases
[name] [name]., Ph.D. – 75 Cases
[name]., Ph.D. – 75 Cases

Principal investigators are responsible for the overall project and performing the surgical procedures in all study groups. Responsible for applying for ethical and management approval, recruitment of patients, obtaining patient consent, managing postoperative care of patients and adverse event reporting.

Study Sponsor

Biomet Korea

Study sponsors take responsibility for initiation, management, and/or financing of a clinical studies at investigational sites.

Study Monitor in Korea

[name]

Study monitors are responsible for carrying out the monitoring procedure as indicated in the protocol.

STUDY OBJECTIVE

The primary objectives of this clinical study include:

- Evaluate size fit and long term performance of Vanguard Complete Knee (“Fixed”) System in Asian and Latino population Compare Vanguard High Flex Rotating Platform (“High Flex”) Knee System to Vanguard Complete Knee System in Asian population in terms of:
 - Early ROM
 - Clinical outcomes
- Compare current design to new design of Vanguard High Flex Rotating Platform Knee System in terms of :
 - Early ROM
 - Clinical outcomes

DEVICE DESCRIPTION

Vanguard Complete Knee

Vanguard Knee is a metal and polyethylene system designed to replace the body's natural knee joint and is indicated for cemented tibial and cementless femoral use. The system contains three (3) primary components and one (1) peripheral component. The primary components include, femoral, tibial, and bearing components, while the peripheral component is the patella button. The use of the patella button is optional.

Vanguard High Flex Rotating Platform Knee (current design)

Vanguard High Flex RP knee is an extension to the existing Vanguard Knee and has been specifically designed to facilitate greater than 135 degrees of knee flexion as required by certain patients. Specifically the Vanguard High-Flex Knee components are required to be able to flex to 150° without point loading or falling off the back of the tibia and to be hyper extended to 15°. It should be noted that this range of motion would only be obtained where the patient had similar flexion and hyperextension ability prior to the arthroplasty. The decision on which rotating platform variant to use is at the discretion of the operating surgeon

Mobile bearing knees are considered advantages as they enable improved congruency between the femoral component and the bearing, compared with a fixed bearing, which results in lower contact stresses of the bearing, thereby reducing wear. Another advantage of mobile bearings is the ability for self-alignment, which reduces wear caused by mal-alignment, enabling the knee to function more naturally and prevents torsion stress on the implant/bone cement/bone interface which may cause loosening.

The tibial tray of the High Flex knee is available in 9 sizes, from 59 to 91mm in 4 mm increments, in interkok finish for cemented applications or with porous plasma sprayed titanium coating for cementless use. It is manufactured from cast cobalt chromium alloy. The stem has a tapered cone geometry for press fit stability. In the cementless option the proximal 1/3 of the stem is porous coated with plasma sprayed titanium. (Note: The tibial trays are manufactured and CE marked by Biomet Spain).

The femoral component is offered in thirteen sizes from 55 to 80mm in 2.5 mm increment, it is anatomic in design (i.e. right and left). It is manufactured from cast cobalt chromium alloy.

The bearing is compression moulded UHMPWE (ArCom). It is matched to the femoral component and is available in 5 thickness from 10-18mm (2mm increments) and 13 sizes from 50mm to 80mm (2.5mm increments). The bearing was designed specifically for the High-Flex to allow rotation of ±8° without overhang.

The patella has an anatomic design and is matched to the thirteen sizes of femoral component patella tracks. It is available in one thickness only. It is compression moulded from UHMWPE (ArCom). Use of the patella button is optional at the discretion of the surgeon.

STUDY DESIGN

[figure not shown]
The study is designed as a prospective, controlled multi-center study including sites from Korea, Japan and Mexico.

To achieve all the primary objectives, the study will include 2 subgroups. The relationship between the two subgroups is illustrated in the following table and graph:

Subgroup	Objectives	Trial Group	Control Group	Design	Endpoint(s)
2	Compare early ROM, Clinical Outcomes, assess Kinetic and Kinematic characteristics between Vanguard Complete Knee System and Vanguard High Flex Rotating Platform Knee System*	Vanguard Complete Knee System w/ std tray (part of subgroup 1 control)	Vanguard High Flex RP (Current Design)	RCT	ROM, AKS,.
4**	Compare early ROM, clinical outcomes and assess Kinetic and Kinematic characteristics between current design and new design of Vanguard High Flex Rotating Platform Knee Systems	Vanguard High Flex RP (New Design)	Vanguard High Flex RP (same as control from subgroup 2)	Historical/concurrent control	ROM, AKS, Survivorship and Fluoroscopic analysis, Gait lab analysis, patella clunk and crepitus.

*Japanese sites will include equal number of Healthy Knees for ROM, Kinetic and Kinematic analysis.

** Subgroup 4 will be initiated once the new design of Vanguard high flex RP is release.

The study will be conducted over a period of 12 to 15 years. Patients from subgroups 2 and 4 will be followed at immediate postop, 6 weeks, 6 months, 1 year, 3 years, 5 years, 7 years and 10 years.

PATIENT SELECTION

All subjects, regardless of sex, race, or geographic location, must fit into the scope of the Inclusion / Exclusion criteria to be eligible for the study. If required per applicable regulations, all participants must sign an Informed Consent to be enrolled into the study.

Inclusion Criteria

In accordance with Indications for Use for Vanguard Complete Knee System and Vanguard High Flex Rotating Platform Knee System specifically:

- Painful and disabled knee joint resulting from osteoarthritis, rheumatoid arthritis, traumatic arthritis where one or more compartments are involved.
- Correction of varus, valgus, or posttraumatic deformity.
- Correction or revision of unsuccessful osteotomy, or arthrodesis.

Patient selection factors to be considered also include:

- Need to obtain pain relief and improve function

- Ability and willingness of the patient to follow instructions, including control of weight and activity level
- A good nutritional state of the patient, and
- The patient must have reached full skeletal maturity

Exclusion Criteria

In accordance with Absolute and Relative Contraindications for use for Vanguard Complete Knee System and Vanguard High Flex Rotating Platform Knee System.

Absolute contraindications include: infection, sepsis, osteomyelitis, and failure of a previous joint replacement.

Relative contraindications include:

- A. Uncooperative patient or patient with neurologic disorders who are incapable of following directions,
- B. Osteoporosis,
- C. Metabolic disorders which may impair bone formation,
- D. Osteomalacia,
- E. Distant foci of infections which may spread to the implant site,
- F. Rapid joint destruction, marked bone loss or bone resorption apparent on roentgenogram,
- G. Vascular insufficiency, muscular atrophy, neuromuscular disease,
- H. Incomplete or deficient soft tissue surrounding the knee.

ENDPOINTS

	SUBGROUP 2	SUBGROUP 4
PRIMARY ENDPOINTS*	Range of Motion at 1 yr postop. AKS at 1 year postop	Range of Motion at 1 yr postop. AKS at 1 year post op
SECONDARY ENDPOINTS	At all follow-up visits: Survivorship American Knee Society Score. Range of Motion Radiographic Assessment Patient Satisfaction – EQ5D Complications including revisions Patella Clunk and Crepitus	At all follow-up visits: Survivorship American Knee Society Score. Range of Motion Radiographic Assessment Patient Satisfaction – EQ5D - OKS - FJS Complications including revisions Patella Clunk and Crepitus

*For sample size calculations.

PARTICIPANT POPULATION (SAMPLE SIZE)

Participant population is determined based on primary/secondary endpoints of each subgroup following superiority or non-inferiority methodologies. Minimum sample sizes are determined in order to prove the hypotheses.

Subgroup 2 - Primary Endpoint Range of Motion at 1 year postoperative
 Superiority test

Null Hypothesis: H_0 $\mu_t = \mu_c$

Alternative Hypothesis: H_a $\mu_t = \mu_c + d$

μ_t : mean of ROM in the trial group (Vanguard Complete Knee) at 1 year postoperative.

μ_c : mean of ROM in the control group (VG RP Knee) at 1 year postoperative.

$\alpha = 0.025$ Significance Level (95% confidence)

$\beta = 0.20$ 80% Power

$d = 5$ (degrees) Clinically Relevant Difference in ROM based on literature and engineering input.

$\xi = 17.5$ Estimate standard deviation of ROM at 1 year postoperative. This value is based on results (preop and 1 year postop) from literature¹

$N = 231$

Consider lost to follow-up at 1 year postop, therefore the adjusted sample size is set as **250 knees per group (a total of 500 knees)**.

Subgroup 2 - Secondary Endpoint AKS at 1 year postoperative
 Non-inferiority test

Null Hypothesis: H_0 $\mu_t = \mu_c$

Alternative Hypothesis: H_a $\mu_t = \mu_c + d$

μ_t : mean of AKS score in the trial group (Vanguard Complete Knee) at 1 year postoperative.

μ_c : mean of AKS score the control group (VG RP Knee) at 1 year postoperative.

¹ [Miner AL](#), [Lingard EA](#), [Wright EA](#), [Sledge CB](#), [Katz JN](#); Knee range of motion after total knee arthroplasty: how important is this as an outcome measure, *J Arthroplasty*. 2003 Apr;18(3):286-94.

$\alpha = 0.025$	Significance Level (95% confidence)
$\beta = 0.10$	80% Power
$Z_{1-\alpha/2} = 1.96$	
$Z_{1-\beta} = 1.28$	
$d = 10$ points	Clinically Relevant Difference in Pain.
$\xi = 15$	Estimate standard deviation of AKS at 1 year postoperative. This value has been based on results from Biomet studies
$N = 48$	
	Consider possible lost to follow-up at 1 year postop, therefore the adjusted sample size is set as 51 knees per group. The final sample size for subgroup 2 is larger of the two sample sizes: 250 knees per group.
	Therefore there will be 250 Vanguard Complete Knee will be compared to 250 Vanguard High Flex RP knee for subgroup 2 study.
	Due to unknown release schedule for new designed VG High Flex RP Knee, sample size of subgroup 4 will be determined at time of the product release. Nevertheless the sample size will be determined based on the comparison to results of 250 VG High Flex RP knee of current design from subgroup 2.

RANDOMIZATION

For subgroup 2 study, patients will be randomized to receive Vanguard Complete Knee (trial group), or Vanguard High Flex RP Knee (control group). Patients have an equal opportunity of being assigned to the trial group or control group. The randomization will occur via a random number generator (manual or computer). The doctor or other health care professional does not choose the participants for each group. For Patients satisfying inclusion criteria, randomization will occur by retrieving the next randomly generated group assignment.

INSTITUTIONS

There will be a maximum of 8 sites from Korea and Japan in subgroup 2. The number of sites for subgroup 4 will be determined once new design of Vanguard High Flex RP is released.

PARTICIPANT DATA MANAGEMENT

The following table summarizes data collection required during the course of the study.

SUBGROUP 2	PRE-OP	SURGERY	IMMEDIATE POST-OP	3 MO	6 MO	1 YR	3 YR	5 YR	7 YR	10 YR
Informed Consent	X									
Demographic	X									

and Historical Record											
Preoperative AKS	X										
Operative Record		X									
Immediate Post-Operative Radiographic Assessment (Bench Mark)			X								
Postoperative AKS (Including ROM)				X	X	X	X	X	X	X	X
Patella Clunk and Crepitus				X	X	X					
EQ5D				X	X	X	X	X	X	X	X
Radiographic Assessment				X	X	X	X	X	X	X	X
Complications & Revisions				Anytime							

SUBGROUP 4	PRE-OP	SURGERY	IMMEDIATE POST-OP	3 MO	6 MO	1 YR	3 YR	5 YR	7 YR	10 YR	
Informed Consent	X										
Demographic and Historical Record	X										
Preoperative AKS	X										
Operative Record		X									
Immediate Post-Operative Radiographic Assessment (Bench Mark)			X								
Postoperative AKS (Including ROM)				X	X	X	X	X	X	X	
Patella Clunk and Crepitus				X	X	X	X	X	X	X	
EQ5D/SF36				X	X	X	X	X	X	X	
Radiographic Assessment				X	X	X	X	X	X	X	
Complications & Revisions				Anytime							

PARTICIPANT EVALUATION SCHEDULES

All study Participants are expected to return for clinical, kinetic and kinematic analysis if any and radiographic evaluation at specific follow-up intervals. The following table summarizes the schedule for post-operative follow-up time intervals:

Evaluation Schedule		
Interval	Follow-Up Window	Months Post-Op Range
Immediate Post-Op	± 2 weeks	Immediate post-op < 2 weeks
3 month follow-up	± 1 month	2-4
6 month follow-up	± 1 month	5-7
1 year follow-up	± 2 months	10-14
3 year follow-up	± 3 months	33-39
5 year follow-up	± 3 months	57-63
7 year follow-up	± 3 months	81-87
10 year follow-up	± 3 months	117 - 123

COMPLICATIONS (ADVERSE EVENTS)

All adverse events, device related (see *Risk Analysis Section*) or non-device related, are to be recorded. Anticipated adverse events are defined, but not limited to, the following:

- Operative side knee manipulations or injections
- Operative side dislocations
- Operative side aspiration of joint fluids
- Falls
- Accidents- motor vehicle, motorcycle, ATV, etc.
- Death
- Any event in which the subject requires hospitalization or outpatient medical attention, including but not limited to: myocardial infarction, cerebral vascular accident, pulmonary emboli, gastrointestinal disorders, or a new diagnosis of a chronic condition (lung disease, renal disease, cancer, diabetes mellitus, hematological abnormalities, etc.).

RADIOGRAPHIC PROTOCOL

1. **Radiographic Views**
The study requires a standard anteroposterior view, mediolateral view, and a skyline patellar view.
2. **Reviewer**
The study investigator will assess his own patient's radiographs.

3. Assessment Procedure

- Assessments will be recorded on the following two radiographic assessment reports:
 - Form XR100 (immediate post-operative)
 - Form XR200 (6 week, 6 month, 1 year, 3 year, 5 year, 7 year and 10 year).
- The radiographic films will be marked for measurements as described in the following “Measurement angles and reference points” section of this document. These “marked” radiographs will be used to determine the implant femoral flexion angle (α), tibial angle (β), total valgus angle (Ω), tibial angle (σ), and femoral flexion (γ).
- The immediate post-operative film will be used as an index for subsequent follow-up assessments.

The radiographic assessment definitions are as follows:

- Anteroposterior Radiograph:
This radiographic view can be obtained with the participant in the standing or recumbent position.
- Mediolateral Radiograph:
This radiographic view can be obtained with the participant in the standing or recumbent position.
- Skyline Radiograph:
This radiograph view can be obtained with the patello-femoral joint in flexion
- Radiolucency or Radiolucent Lines:
A radiographic clearing or line not exceeding 2mm in width at the bone/cement or cement/implant interface
- Osteolysis:
A progressive radiolucency > 2mm in **two or more** zones not present on immediate postoperative radiographs and/or a bony destructive lesion that is progressive in nature.
- Migration/Subsidence:
A component migration of > 3 mm or > 3° as compared to immediate post-operative radiographs is considered a failure.

DATA COLLECTION

All sites will be required to complete and submit case report forms on Biomet’s online database, Joint Assist 2.0, in a timely manner. Forms will be monitored for completeness and accuracy.

Further, it is imperative that the investigator answers all questions on the case report forms. All data should be accurate, indelible, legible, dated on the date of entry, and signed by initials, and/or formal signature by the authorized personnel documenting the data.

MONITORING PLAN

Prior to commencing the study the Monitor will provide the investigators with the necessary information to enable him/her to carry out his responsibilities. This information includes but not limited to:

- Investigator Brochure i.e. study protocol, investigator responsibilities, device information, etc.

- Ethical Committee Approval Information.
- Case Report Forms.
- Patient Consent Forms
- EDC user manual

The monitor of the evaluation periodically reviews the post-operative follow-up dates on all subjects for each evaluator. A follow-up schedule is then sent to each investigator, which illustrates any follow-up, reports which are due or missing. Every effort is made to assure that follow-up reports are completed in a timely manner, including contacting the evaluator by post, telephone or by personal visit when necessary. Also, during the course of the evaluation, the monitor will conduct periodic discussions with the investigator or staff to ensure that the evaluation is being conducted in accordance with the protocol. The monitor will maintain records of each visit or discussion.

CONFIDENTIALITY

To ensure study patients' privacy, all patients will be identified by unique identification numbers. All case report forms will only include patient IDs. It is the responsibility of the investigator to maintain a list of patient identification and Joint Assist 2.0 ID numbers.

Further the Joint Assist database is restricted, allowing a doctor to only view and enter data from his own patients. User authentication is required to view research data. The data is transmitted to a centralized database through a secured (SSL) channel on the Internet. Data in transit is in 128-bit encryption. The access to the centralized database is limited to those who are responsible for maintaining the database.

RISK ANALYSIS

This clinical study is to collect data on the Vanguard DD RP Knee, which is intended to help the participant gain mobility and decrease pain. Risks associated with this knee system include general surgical and knee arthroplasty risks. Due to the investigational nature of the system, there are unknown risks.

General Surgical Risks

As with any surgical procedure, there are risks involved with total joint replacement surgery. Potential adverse events include, but are not limited to: early or late infection perhaps necessitating device removal; component dislocation; damage to nerves and blood vessels; fracture of the bone or device; device loosening; allergic reactions to the metallic devices; phlebitis; long-term swelling; pulmonary embolization; and delayed wound healing. Other potential adverse effects include: prolonged illness; hematoma; wound dehiscence and/or drainage; the need for blood transfusions and/or further surgery; or permanent pain; deformity; and inconvenience. Risks associated with the anesthetic are those such as permanent brain damage, pneumonia, blood clots, and heart attack. Rarely some adverse events may be fatal. These possible adverse events are not unique to the Vanguard™ RP System and, as stated above, may occur with any total joint replacement surgery.

As with any joint replacement post-operative activity, limitations may be imposed

depending upon the participant's age, general health, baseline (pre-operative) activity level and baseline (pre-operative) condition of the knee and other joints.

Potential Risks Associated with Vanguard™ RP Knee System

The safety and efficacy of the Vanguard™ RP Knee System has not been thoroughly demonstrated clinically, participants participating in the study may be subject to increased risks and/or adverse events including, but not limited to:

1. Material sensitivity reactions
2. Early or late post-operative infection and/or allergic reaction
3. Intra-operative bone perforation or fracture
4. Loosening or migration of implants
5. Periarticular calcification or ossification, with or without impediment of joint mobility
6. Inadequate range of motion
7. Dislocation or subluxation of device
8. Fatigue fracture of components
9. Fretting or corrosion of implant interfaces
10. Wear and/or deformation of articulating surfaces
11. Valgus/Varus deformity
12. Transient peroneal palsy secondary to surgical manipulation and increased joint movement
13. Patellar tendon rupture and ligamentous laxity
14. Intra-operative or post operative bone fracture
15. Post operative pain and/or delayed wound healing
16. Inadequate lubrication
17. Implant of the device may require a more demanding implantation procedure with greater surgical exposure and prolonged surgical time
18. Damage to surrounding tissues, cartilage, or tendons

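### OKS and FJS are subgroup 4 endpoints but are scheduled in neither subgroup and are not endpoints of its control knees; EQ5D is shared after surgery but has no pre-op value

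*Combined protocol and SAP*

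**What the plan says.** All references are to the combined protocol and SAP.

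- **Who the control is.** The subgroup table under STUDY DESIGN names subgroup 4's control as "Vanguard High Flex RP (same as control from subgroup 2" and its design as "Historical/concurrent control". The sample size section agrees: "the sample size will be determined based on the comparison to results of 250 VG High Flex RP knee of current design from subgroup 2".
- **When it starts.** The table footnote says "Subgroup 4 will be initiated once the new design of Vanguard high flex RP is release".
- **Endpoints.** The ENDPOINTS table sets these at every follow-up visit. The subgroup 2 list reads "Patient Satisfaction – EQ5D Complications including revisions Patella Clunk and Crepitus". The subgroup 4 list reads "Patient Satisfaction – EQ5D - OKS - FJS Complications including revisions Patella Clunk and Crepitus". The primary endpoints are the same in substance for both; the subgroup 2 cell reads "Range of Motion at 1 yr postop. AKS at 1 year postop".
- **Schedules.** Under PARTICIPANT DATA MANAGEMENT, the subgroup 2 table has an EQ5D row and the subgroup 4 table has a row labelled EQ5D/SF36. Neither table has an OKS or FJS row. The only outcome score with a pre-op row, in both tables, is "Preoperative AKS".

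**The concern.** Subgroup 4 exists to compare two designs, and its comparator is a set of knees enrolled for another question on another schedule. An endpoint that these knees do not provide cannot enter the comparison, however carefully it is collected in the new-design knees. Adding rows to the subgroup 4 table alone would still leave the control empty.

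Timing makes this more pressing. Subgroup 4 waits for a product release of unknown date, so control visits may pass before the gap is noticed, and a questionnaire not given at 3 months or 1 year cannot be given later. The comparison is also not randomised, so a pre-op value matters more here than in subgroup 2, where randomisation balances starting quality of life on average.

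**Working it through.** No figure in the plan needs reproducing. The main check sets the ENDPOINTS table beside the two data-collection tables.

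| Instrument | Subgroup 4: endpoint / scheduled | Subgroup 2 control: endpoint / scheduled | New-versus-current comparison as written |
|---|---|---|---|
| OKS | yes / no | no / no | none |
| FJS | yes / no | no / no | none |
| SF36 | no / yes, sharing a row with EQ5D | no / no | none, and not an endpoint |
| EQ5D | yes / yes, post-op | yes / yes, post-op | post-op levels only |
| AKS with ROM | yes / yes, AKS also pre-op | yes / yes, AKS also pre-op | intact |

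**OKS and FJS.** If the schedule governs, neither is collected in any knee. If the endpoint list governs, they are collected in new-design knees only. In both cases 0 of the 250 planned control knees have a value at any of the seven follow-up visits (3 and 6 months; 1, 3, 5, 7 and 10 years).

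**EQ5D baseline.** The subgroup 2 EQ5D row, as extracted, has eight marks for seven follow-up columns. The postoperative AKS row has the same surplus mark, so it is not evidence of a pre-op EQ5D.

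**What the missing baseline costs.** The documents give no baseline/follow-up correlation *r*, so *r* = 0.3 to 0.5 is assumed.

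- Variance of a post-only comparison relative to a baseline-adjusted one is 1/(1 − r²). At r = 0.3 this is 1/(1 − 0.09) = 1.10; at r = 0.5 it is 1/(1 − 0.25) = 1.33.
- Bias from an unseen baseline gap of D standard deviations (SD) is about r × D. For an assumed D = 0.2 this is 0.3 × 0.2 = 0.06 SD to 0.5 × 0.2 = 0.10 SD. For D from 0.1 to 0.3 the range is 0.03 to 0.15 SD.
- For scale, the difference detectable with 80% power at two-sided 5% is (1.96 + 0.8416) × √(1/250 + 1/n₄). Subgroup 4's size n₄ is not set. If it were 250, this would be 2.8016 × √0.008 = 0.25 SD, ignoring losses.

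Under these assumptions the bias is smaller than the detectable difference but not negligible.

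**The case against.** The strongest reply is that little of importance is lost. In the STUDY DESIGN table, subgroup 4's endpoint column lists no patient-reported instrument. ROM and AKS at 1 year are primary and are collected in both subgroups, so the comparison of clinical outcomes survives through AKS. Subgroup 4's size and sites are deferred to product release, which leaves room for an amendment, and the control may be partly concurrent. All of this stands, and it keeps the point at the level of secondary endpoints. It does not supply OKS or FJS data: concurrent controls would still be subgroup 2 knees on the subgroup 2 schedule.

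A reader might infer more than the documents support:

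- **That EQ5D cannot be compared either.** It is scheduled at the same post-op visits in both subgroups. Change from baseline and adjustment for baseline quality of life are lost; a cross-sectional comparison is not. Pre-op AKS and the demographic and historical record allow some adjustment.
- **That SF36 is a third endpoint without a control.** It is only a schedule label. By endpoint the count is two of three.
- **That OKS and FJS will at least describe the new design.** The subgroup 4 schedule does not collect them.
- **That the slash lets sites replace EQ5D with SF36.** It may equally mean both; the text does not settle it.
- **That the control's early visits are already past.** The documents leave this open.

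**Conclusion.** The point holds for OKS and FJS: both are named secondary endpoints of subgroup 4, neither is scheduled in either subgroup, and neither is an endpoint of the control knees. This follows from reading the tables together and needs no statistical assumption.

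For EQ5D the finding is a weakness only. The comparison is possible but cannot be adjusted for starting quality of life. The illustrative cost is 0.06 to 0.10 SD of bias and 1.10 to 1.33 times the variance. It rests on the assumed correlation of 0.3 to 0.5 and, for the bias, on an assumed 0.2 SD gap; adjustment for pre-op AKS might remove part of it. It is also unclear whether EQ5D is required in every subgroup 4 patient.

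The primary comparison on ROM and AKS at 1 year is not affected. This is a cheap improvement, not a threat to the study's main conclusions.

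**What to change.** 1. Add OKS and FJS rows at every follow-up visit to **both** data-collection tables, and list both as subgroup 2 secondary endpoints. Changing only one table leaves one side of the comparison empty.
2. Add EQ5D and OKS at the pre-op visit in both subgroups, and state that the new-versus-current comparisons of EQ5D and OKS are adjusted for the pre-op value.
3. In the subgroup 4 table, make EQ5D mandatory for every patient. Either drop SF36 or give it its own row, labelled descriptive.
4. Where control visits have already passed, label OKS and FJS as descriptive outcomes of the new design only and keep them out of the new-versus-current comparison. They still need rows in the subgroup 4 table.

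The cost is a few minutes of patient time at visits already planned and an update to the case report forms. Beyond the subgroup 4 rows, the fallback in item 4 costs only wording.

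### No pre-operative EQ5D is scheduled in either subgroup, and its satisfaction label has no defined item or scoring: a cheap improvement to a secondary endpoint

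*Combined protocol and SAP*

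**What the plan says.** The Endpoints table places EQ5D among the secondary endpoints as "Patient Satisfaction – EQ5D", under the heading "At all follow-up visits". For subgroup 2 the entry runs "Patient Satisfaction – EQ5D Complications including revisions", so EQ5D is the only instrument under the satisfaction label before the list moves on. For subgroup 4 it reads "Patient Satisfaction – EQ5D - OKS - FJS".

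In Participant Data Management, each subgroup has a collection table with columns from PRE-OP to 10 YR. Only three rows carry a pre-operative mark in either table: consent, the demographic and historical record, and "Preoperative AKS". The EQ5D row in subgroup 2 and the EQ5D/SF36 row in subgroup 4 start at 3 months. OKS and FJS have no row. SF36 has one, but it is not in the endpoint list.

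The Study Design table makes subgroup 2 a randomised comparison. It gives subgroup 4 a historical or concurrent control, namely the High Flex RP knees from subgroup 2. The documents do not say how EQ5D is scored or analysed, do not define a change from baseline in it, and name no satisfaction question or scale.

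**The concern.** A site that follows the tables will never obtain a pre-operative EQ5D, although it takes a pre-operative AKS at the same visit. Three things follow.

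- Post-operative EQ5D cannot be adjusted for its own starting value, and EQ5D gain from surgery cannot be described.
- In subgroup 4 randomisation does not balance starting health. The control knees come from subgroup 2, so a baseline missed now is also missing for the later comparison. It cannot be measured after surgery. Adding the form only when subgroup 4 opens would cover one side of that comparison.
- A result reported under the satisfaction label would have no defined satisfaction measurement behind it.

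**Working it through.** The plan gives no EQ5D figure to reproduce: its sample sizes rest on ROM and AKS. The check is a reading of the schedule, followed by two illustrations under stated assumptions.

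**1. Schedule.** Rows set against the column headings:

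| Row | PRE-OP | SURGERY | IMMEDIATE POST-OP | 3 MO to 10 YR (7 columns) |
|---|---|---|---|---|
| Pre-operative AKS, both subgroups | X | blank | blank | blank |
| Post-operative AKS, subgroup 2 | blank | blank | blank | 8 X |
| EQ5D, subgroup 2 | blank | blank | blank | 8 X |
| EQ5D/SF36, subgroup 4 | blank | blank | blank | 7 X |

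The subgroup 2 row, "EQ5D X X X X X X X X", has one X more than the seven columns left for it. This is not a hidden baseline mark. The row beginning "Postoperative AKS (Including ROM" is post-operative by definition and has the same surplus, as does the radiographic row, and the subgroup 4 row aligns exactly. The surplus is probably an artefact of text extraction. Study Design mentions a 6-week visit where the tables have 3 months, but either is after surgery. Planned pre-operative EQ5D values: 0 of 500 knees in subgroup 2, and none in subgroup 4, whose size is still to be set.

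**2. Precision in subgroup 2.** Assumed, not in the documents: pre/post correlation r of 0.3 to 0.5. With adjustment for baseline, residual variance is multiplied by 1 − r² and the standard error by √(1 − r²).

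- r = 0.3: 1 − 0.09 = 0.91, a 9% cut in variance; √0.91 = 0.954, about 5% off the standard error.
- r = 0.5: 1 − 0.25 = 0.75, a 25% cut in variance; √0.75 = 0.866, about 13% off the standard error.

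As a standardised detectable difference, take 250 knees per group (the planned number), and assume two-sided 5%, 80% power, no losses and independent knees:

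(1.960 + 0.842) × √(2/250) × √(1 − r²)

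This gives 0.251 SD without a baseline, 0.239 at r = 0.3 and 0.217 at r = 0.5. At the unadjusted sample size of 231 the figures are 0.261, 0.249 and 0.226. EQ5D describes a patient, and the documents count knees without saying how many patients they represent, so these are illustrations only.

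**3. Carry-over in subgroup 4.** If mean starting EQ5D differs between the groups by Δ, the post-operative comparison shifts by slope × Δ with no design effect at all, where slope = r × SD_post/SD_pre. With Δ in pre-operative SD units and the shift in post-operative SD units, this reduces to r × Δ. On the raw scale it equals r × Δ only if the two SDs are equal. For an assumed Δ of 0.2 SD the shift is 0.3 × 0.2 = 0.06 SD to 0.5 × 0.2 = 0.10 SD before any covariate adjustment. Adjusting for pre-operative AKS and demographics may remove part of it. The documents give no basis for saying how much.

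**4. Label.** In subgroup 2 the satisfaction label covers EQ5D alone. In subgroup 4 it covers EQ5D, OKS and FJS, while the schedule supplies EQ5D/SF36. The two lists share only EQ5D, and neither subgroup has a named satisfaction item or a rule for deriving one.

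**The case against.** The strongest reply is that the schedule delivers what the Endpoints table asks for. The secondary endpoints are defined at follow-up visits, and no EQ5D change from baseline is promised. That stands. A reader might infer that the plan contradicts itself or cannot produce its EQ5D endpoint. The documents do not support this: the omission is a design gap.

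A reader might also infer that the EQ5D comparison in subgroup 2 is invalid. It is not. Random allocation makes a comparison of post-operative values sound, and only precision and any statement about improvement are lost. EQ5D also has no hypothesis, margin or sample size, and it appears neither in the Study Objective nor in the endpoint column of the Study Design table. This limits the weight of the point.

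For subgroup 4, a reader might infer that starting health cannot be separated from a design effect at all. That goes too far, because pre-operative AKS and demographics are collected in both subgroups and permit partial adjustment. What remains is that starting EQ5D itself can be neither compared nor adjusted for directly.

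On the label, the view that EQ5D measures health status and not satisfaction is general knowledge of the instrument, and the documents do not state it. They show something narrower: no satisfaction item, scale or scoring is defined. That is enough to justify relabelling.

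**Conclusion.** The point holds as a cheap improvement to a secondary endpoint. It does not touch the primary endpoints, ROM and AKS at 1 year. That no baseline is planned follows from the tables alone. The precision gain in subgroup 2 is modest and rests entirely on the assumed correlation. It also applies only to patients who have not yet had surgery. The case for acting is stronger in subgroup 4, where the control is not randomised and its missing baselines cannot be recovered later. The size of any confounding there is unknown, and the 0.06 to 0.10 SD shift depends on an assumed imbalance. The labelling point rests on what the documents leave undefined.

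**What to change.** 1. In both Participant Data Management tables, add an X under PRE-OP for EQ5D. State in the protocol that post-operative EQ5D will be compared between groups adjusted for the pre-operative value.
2. For patients already operated on, including those who will serve as subgroup 4 controls, analyse post-operative EQ5D only, adjust for pre-operative AKS and demographics, and say plainly that starting EQ5D is unknown for them. The new form cannot cure the gap for these patients, which is a reason to add it soon.
3. In the Endpoints table, replace the satisfaction label with health status or patient-reported outcome, for EQ5D in both subgroups and for OKS and FJS in subgroup 4.
4. Reconcile the subgroup 4 endpoint list (EQ5D, OKS, FJS) with its schedule row (EQ5D/SF36), so that each listed instrument has a row and each row has an endpoint.

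The cost is one short questionnaire at a pre-operative visit that already takes consent, history and AKS, plus wording changes.
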